1 PROTOCOL SUMMARY

1.1 Synopsis

- Title:** Phase 2 study of the PTH-independent Effects of Encaleret on Mineral Homeostasis in subjects with post-surgical hypoparathyroidism (PSH)
- Study Description:** This will be a single-site, proof-of-principle, open-label study to explore the PTH-independent effects of encaleret on calcium homeostasis in participants with low or undetectable PTH levels as a result of neck surgery (PSH).
- Objectives:** *Primary Objective:*
- Evaluate the PTH-independent effects of encaleret on renal calcium handling in participants with PSH.
- Secondary Objectives:*
- Evaluate the ability of encaleret to normalize blood calcium while maintaining a normal urinary calcium in participants with PSH.
- Tertiary/Exploratory Objectives:*
- Evaluate the ability of encaleret to increase serum iPTH levels in participants with PSH.
 - Evaluate the effect of encaleret on 1-alpha hydroxylase action by measuring 1,25-(OH)₂ Vitamin D levels.
 - Explore the dynamic effect of encaleret on blood and urinary calcium, iPTH, cAMP, 1,25-(OH)₂ Vitamin D, and urinary citrate.
 - Evaluate the effect of encaleret on bone turnover in participants with PSH.
 - Evaluate the effect of encaleret on phosphate, magnesium, and FGF23 levels.
 - Explore the effects of encaleret on 24-hour urine markers that impact stone formation
 - Examine the PK of encaleret in participants with PSH and explore PK-PD interactions.
 - Explore the effect of encaleret on bone and mineral homeostasis in the following sub-groups, *as defined in Section 9.3:*
 - Permanent hypoparathyroidism (Cohort 1)
 - Recent hypoparathyroidism (Cohort 2)
 - “PTH-Clamp” cohort
 - “Aparathyroid” cohort
 - Hyperthyroid cohort
 - Normothyroid cohort
 - Thyroid cancer cohort

2

Primary Endpoint:

- Percent change in Fractional Excretion of Calcium (FECa) from baseline (Day -1) to the final day of treatment (Day 6 or the last measurement while on encaleret). FECa calculated using fasting blood levels and spot urine collection.

Secondary Endpoints:

- Proportion of participants who achieve a concomitant normal or elevated fasting blood calcium (albumin-corrected calcium >8.5 mg/dL) and a normal 24-hour urinary calcium level (<250 mg/24 hours for women, <300 mg/24 hours for men) on encaleret at any point between day 1 and day 5.

Tertiary/Exploratory Endpoints:

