Participants who complete the screening visit midweek have the option to stay overnight at NIH CC (or at local housing) during the intervening days prior to the start of Day -1. Participants also have the option of travel to be local to the NIH on day -2 and stay at NIH housing (e.g., The Edmond J. Safra Family Lodge) if available. Participants have the option of being admitted on Day -2 or Day -1.

² Vital signs include supine or sitting blood pressure (BP) by automated cuff, heart rate (HR), and respiratory rate, to be collected q8 hours during in-patient days.

³ Algorithm for calcium/calcitriol titration and encaleret stopping criteria found in Table D

⁴ Screening lab tests: CBC, Acute care panel, ionized calcium, eGFR, Liver Function Panel, mineral panel, iPTH, 25-OH Vitamin D, Lipid panel, CK, LDH, amylase, lipase, uric acid, Coagulation (PT/PTT/INR), urinalysis, HIV, Viral Hepatitis panel, FSH level test (postmenopausal women), spot urine: calcium, magnesium, phosphate, creatinine, and cAMP. TSH, Free T4

⁵ Safety lab tests: BMP, calcium, albumin, magnesium, phosphate, iPTH.

⁶ See Table B and C. Note attempts will be made to collect fasting calcium levels prior to the morning calcium dosage, however, calcium will be given to participants if clinically indicated (for example, in the setting of hypocalcemia).

⁷ Participants instructed to obtain outpatient laboratory testing, approximately 3-7 days after discharge from NIH CC.

⁸ Research team will contact the subject to review test results and provide guidance regarding clinical management as they transition to prior clinical care providers.

⁹ All participants will receive a FU call within 30 ± 7 days after last dose of the encaleret. If subject discontinues from the study early (ET), they will resume prior medication regimen, and study team will arrange FU labs within 3-7 days and FU calls at 30 ± 7 days and 90 ± 7 days after the last dose of encaleret as long as subject agrees.

¹⁰ Final close out phone call will assess for any unintended pregnancies in either the patient or a sexual partner.

Table B: Urine Assays

	Day 1-5 Timepoints relative to AM dose +/- 20 min. PM dose given at +12 hrs +/- 30 min, given after 12 hr timepoint lab draw
Daily Urine Assays	
Spot Urine Measurement Ca, Mg, PO4, Cr, cAMP	Day -1 (fasting) Day 1, Time 0
Osmolality, cAMP	Day 1, Time 0 Day 1-5: 16-24 hr
Timed Interval Urine Ca, Mg, PO4, Crvolume	Day 1-5: 0-4 hr, 4-12 hr, 12-16 hr, 16-24 hr

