24-Hour urine: Ca, Mg, PO4, Cr, Na, K, pH, Citrate Supersaturation Panel	Days -1 to 5 0-24 hrs (Start collection after first morning void and end 24 hours later) Day -1 and Day 5

Table C: Blood Sampling Days -1 to 5

Day -1: Baseline fasting labs including CBC, acute care panel, intact PTH, Ca, PO4, Mg, Cr, albumin, K, CK, Research blood, Bone turnover markers (CTX, P1NP), 25-(OH) Vitamin D, 1,25-(OH)₂ Vitamin D, cAMP, ionized calcium, TSH, FT4

		-30 min	-15 min	30 min	1 hour	2 hour	4 hour	12 hour	16 hour	24 hour
Day 1	Mineral labs	X	X	X	X	X	X	X	X	
	Safety Labs		X					X		
	Ionized Calcium		X				X	X	X	
	Research Blood	X	X			X	X	X	X	
	Bone Turnover Markers		X							
	1,25D	X	X							
	cAMP		X							
	Pk		X			X	X			
Day 2-4	Mineral labs		X	X			X	X	X	
	Safety Labs		X					X		
	Ionized Calcium		X				X	X	X	
	Research Blood		X				X	X	X	
	Bone Turnover Markers		X							
	1,25D		X							
	cAMP		X							
	Pk		X							
Day 5	Mineral labs		X	X	X	X	X	X	X	X
	Safety Labs		X					X		
	Ionized Calcium		X				X	X	X	X
	Research Blood		X			X	X	X	X	X
	Bone Turnover Markers		X							
	1,25D		X							X
	cAMP		X							X
	Pk		X			X	X			

Mineral Labs: Intact PTH, Ca, PO4, Mg, Cr, Albumin

Safety Labs: Acute care panel (Na, K, Cl, CO₂, BUN, Cr, eGFR), CK

Research Blood

Bone turnover Markers: CTX, P1NP

1,25-(OH)₂ Vitamin D, cAMP

a

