3 OBJECTIVES AND ENDPOINTS

OBJECTIVES	ENDPOINTS	JUSTIFICATION FOR ENDPOINTS
Primary		
Evaluate the PTH-independent effects of encaleret on renal calcium	Percent change in Fractional Excretion of Calcium (FECa) from baseline (Day -1) to the final day	FECa reflects the relationship between blood calcium and

OBJECTIVES	ENDPOINTS	JUSTIFICATION FOR ENDPOINTS
handling in participants with PSH.	of treatment (Day 6 or the last measurement while on encaleret). FECa calculated using fasting blood levels and spot urine collections.	urinary calcium. CaSR modulation by encaleret is expected to directly affect FECa. If a patient stops encaleret early prior to Day 6, the last fasting FECa on encaleret 162 mg BID will be used for this endpoint.
Secondary		
Evaluate the ability of encaleret to normalize blood calcium while maintaining a normal urinary calcium in participants with PSH.	Proportion of participants who achieve a concomitant normal or elevated fasting blood calcium (albumin-corrected calcium >8.5 mg/dL) and a normal 24-hour urinary calcium level (<250 mg/24 hours for women, <300 mg/24 hours for men) on encaleret at any point between day 1 and day 5.	Clinically relevant endpoint to determine if encaleret can allow PSH to have both normal blood and urinary calcium.
Tertiary/Exploratory		
Evaluate the ability of encaleret to increase serum iPTH levels in participants with PSH.	Change in blood iPTH comparing average baseline iPTH to average peak iPTH on encaleret. The average baseline iPTH will include all baseline iPTH levels from the screening visit, Day -1, and pre-dose on Day 1. The average peak iPTH will average the peak iPTH levels on every day the patient is on encaleret (days 1 to 5). An increase in iPTH will be	Averaging iPTH will prevent spurious excursions from impacting outcomes

OBJECTIVES	ENDPOINTS	JUSTIFICATION FOR ENDPOINTS
	considered clinically significant if there is an increase both by 50% AND by more than 10 pg/dL.	
Evaluate the effect of encaleret on 1-alpha hydroxylase action by measuring 1,25-(OH) ₂ Vitamin D levels.	Change in 1,25-(OH) ₂ Vitamin D on encaleret comparing the maximal level prior to receiving calcitriol (On Days 3-5) to baseline (Average of Day 1 Pre-dose levels). Increase will be considered significant if there is an increase of more than 50%. Participants who receive calcitriol prior to Day 3 will be excluded.	

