Day -2 or Day -1 (Admission): Participants will be admitted to the NIH CC either the day prior to dosing or two days prior to dosing based on subject convenience. All participants will be instructed to stop taking calcitriol and home calcium dosage, with last doses on Day -2. Participants on magnesium or potassium citrate will be instructed to stop these supplements, with last doses on Day -3. Calcium supplementation with calcium carbonate(500 mg elemental calcium) three times a day will start on Day -1. Baseline 24-hour urine will be opened the morning of Day -1, and fasting laboratory assessment will be obtained. Attempts will be made to collect fasting calcium levels prior to the morning calcium dosage, however, calcium will be given to participants if clinically indicated (for example, in the setting of hypocalcemia).

Days 1 to 5: Encaleret 162 mg BID will be taken orally by the patient. Detailed summary of planned calcium and calcitriol therapy is presented in Figure 2 and a dosing algorithm is presented in Table D. Frequent blood and urine sampling for 24-hours will be performed for safety and outcome measures (see [Table A and Table B](#)). Encaleret will be administered in the morning and evening with water approximately 12 hours between each dose. The last dose of study medication will occur on the evening of Day 5. Daily ECG will be performed for monitoring of QT interval.

Day 6 (Discharge): After the blood sampling is collected on the morning of Day 6 and the 24-hour urine is closed, all participants will resume their prior conventional treatment regimen. During Day 6, cCa levels will be monitored until the patient is discharged. This admission can be extended if additional monitoring or treatment (e.g., to stabilize calcium) is needed prior to discharge.

Follow-up:

Outpatient testing done on day 8-12 (Less than 7 days after expected discharge from the NIH clinical center) will be collected either at the NIH CC or local laboratory. Blood samples collected will be evaluated for blood creatinine, albumin, calcium, magnesium, phosphate, and PTH. A telephone contact to the patient will be conducted once calcium results are available to be reviewed with investigative team. Additional outpatient testing to follow up safety issues will be performed as needed.

An additional two telephone contacts will be performed at 30-days (\pm 7 days) and 90-days (\pm 7 days) after the last encaleret dose for screening of AEs and pregnancies, respectively.

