8.2.1 Biospecimen Evaluations

Screening visit and inpatient blood samples except for research samples and PK samples will be managed by the NIH Clinical Center laboratory. Urine samples will be either managed by the NIH laboratory or sent to LabCorp. Only exploratory end points, for example FGF23, will

be performed in non-CLIA certified labs on research samples. The primary endpoint assessments include evaluations of urinary excretion of calcium. The times for collection of these samples are detailed in the Schedule of Activities in Section 1.3.

All PK blood samples will be analyzed by a CRO contracted by the manufacturer. Details for sample processing and handling will be provided in a written SOP. The times for collection of these samples are detailed in the Table B and C.

The total blood volume collected for each subject will be less than the blood volume limits per subject as per NIH Guidelines for Blood Draw Limits for Research Purposes (M95-9, June 2009). If a subject has a low body weight (<50 kg for adults), the blood volume taken will be reduced to remain within the NIH guidelines of 10.5mL/kg/8w.

In order to characterize both the pre-study calcemic status as well as changes associated with experimental interventions, the protocol will rely on frequent measurement of albumin-corrected blood calcium concentrations. Assays will be conducted according to specifications of the NIH Clinical Center Laboratory, Bethesda, MD. The main indicator of normal versus abnormal blood calcium levels will be based on the correction for serum or plasma albumin according to the formula corrected calcium (cCa) = measured total calcium (mg/dL) + 0.8(4 – albumin (g/dL)) OR measured total calcium (mmol/L) + 0.2(4 – albumin (g/dL)), recognizing that the total calcium reported in SI units (mmol/L) can be converted to conventional units (mg/dL) by multiplying by 4. Given that enrolled participants are expected to have both normal and stable albumin levels, the measures of total calcium and cCa are likely to be similar throughout the time course of this study. Ionized calcium assays will also be measured at the NIH Clinical Center and can be used to assess calcium status for dose adjustment decisions on a case by case basis in addition to the albumin corrected-calcium.

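### The primary endpoint needs an on-drug fasting spot-urine FECa, but every spot urine calcium and creatinine in the schedule is taken before dosing starts.

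*Combined protocol and SAP*

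**What the plan says.** Sections 1.1 and 3 define the primary endpoint as the percent change in FECa from Day -1 to Day 6, or to the last measurement on drug. Section 1.1 fixes the specimens: "FECa calculated using fasting blood levels and spot urine collection". For a participant who stops early, Section 3 says that "the last fasting FECa on encaleret 162 mg BID will be used for this endpoint". Sections 9.2 and 9.4.2 carry the same rule.

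For collection times, Section 8.2.1 refers to the schedule: "The times for collection of these samples are detailed in the Schedule of Activities in Section 1.3". In Section 1.3:

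- Table B, spot urine (Ca, Mg, PO4, Cr, cAMP): "Day -1 (fasting) Day 1, Time 0".
- Table B, timed interval urine (including Ca and Cr): "Day 1-5: 0-4 hr, 4-12 hr, 12-16 hr, 16-24 hr".
- Table B, 24-hour urine (including Ca and Cr): collected for Day -1 and each of Days 1 to 5.
- Table A: spot urine appears only in the footnote on screening tests. No urine row is marked on Day 6.
- Table C: mineral labs are drawn 15 minutes before the morning dose on Days 1-5 and 24 hours after the Day 5 morning dose.

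Section 8.2 describes the Day 6 morning as "After the blood sampling is collected on the morning of Day 6 and the 24-hour urine is closed" and names no separate void.

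Two other places bear on this. Section 6.1.2 makes a fall of more than 40% in fasting FECa part of the threshold at which the drug may be stopped early. Section 9.1 computes FECa in another way, from 24-hour urine and blood drawn 4 hours after a meal.

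**The concern.** A team that follows Section 1.3 exactly will have the baseline half of the primary endpoint and the closing blood sample, but no closing spot urine. The final FECa must then come from some other urine. The plan does not say which one, so the choice could be made after results are known, or could differ between participants.

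The trial has no control arm and tests the mean percent change against zero. A comparison of a spot sample at baseline with a pooled sample on treatment mixes drug effect with any difference between the two kinds of collection, and nothing in the design separates them. Early stoppers have the same gap, and so does the 40% threshold in Section 6.1.2. The exploratory screening-to-Day 6 FECa lacks the same closing sample.

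**Working it through.** **1. Required specimens against scheduled specimens.**

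| Time | Needed for the primary FECa | Fasting blood scheduled | Spot urine Ca/Cr scheduled | Other urine with Ca/Cr |
|---|---|---|---|---|
| Day -1 | yes (baseline) | yes | yes | 24-hour urine; no timed pools |
| Day 1, Time 0 | no | yes | yes | – |
| Mornings of Days 2-5 | yes, for early stoppers | yes (-15 min) | no | 16-24 hr pool and 24-hour urine of the day before |
| Morning of Day 6 | yes | yes (+24 hour) | no | 16-24 hr pool and 24-hour urine of Day 5 |

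Scheduled spot samples: three (screening, Day -1, Day 1 Time 0). On-drug spot samples: zero.

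**2. Nearest substitute.** The evening dose is given at +12 h, after the 12 h draw. The 16-24 hr pool therefore covers 16 - 12 = 4 to 24 - 12 = 12 hours after that dose, and the blood drawn at its close is 12 hours after it. Participants take no food from midnight, so the pool is probably largely fasting; the clock time of the morning dose is not given. FECa can be computed from this pair. Timed pools start on Day 1, however, so Day -1 has no matching pool. Only the 24-hour urine exists both before and on drug: "Days -1 to 5 0-24 hrs (Start collection after first morning void and end 24 hours later").

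**3. The definition in Section 9.1.** Its urine half is collected at both ends. Its blood half is not: Day -1 has fasting labs and an evening mineral panel, with no draw tied to 4 hours after a meal. That definition cannot be computed at baseline either.

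**4. The plan's own power figures.** Inputs from Section 9.2: two-sided alpha 0.05, paired t-test, SD 20%, 80% power. With noncentrality d√n / SD and n - 1 degrees of freedom, the detectable change d is:

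- n = 15: 15.6% (stated 16%)
- n = 10: 19.9% (stated 20%)
- n = 5: 33.6% (stated 34%)

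The stated figures reproduce after rounding up, and they do not depend on the missing specimen.

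**5. What a method difference could do.** The documents give no value, so this is an assumption shown over a range. Suppose the drug has no effect and the change of collection type alone shifts the mean percent change by b points, with n = 15. The noncentrality is b√15 / SD; for b = 10 and SD 20 it is 10 × 3.873 / 20 = 1.94. Probability that the two-sided 5% test rejects:

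| b (points) | SD 20 | SD 30 |
|---|---|---|
| 5 | 14.7% | 9.2% |
| 10 | 43.8% | 22.5% |
| 15 | 77.1% | 43.8% |

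**6. At the planning effect.** With mean -66% and SD 20%, the 95% half-width at n = 15 is 2.145 × 20 / √15 = 11.1 points. A shift toward zero of about 66 - 11 = 55 points would be needed to lose significance. A modest shift would pass almost unchanged into the estimate.

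**The case against.** The best reply is that usable data exist. The Day 5 16-24 hr pool is assayed for calcium and creatinine, closes on the morning of Day 6, and can be paired with the 24-hour blood; earlier days have the same arrangement. This stands. A reader might infer from Table B that the final FECa cannot be computed at all, and the documents do not support that. What is missing is a specimen of the defined type that matches the baseline.

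A reader might also infer that the pool would overstate the fall, because it covers 4-12 hours after a dose while a morning spot is near trough, and Section 2.2 describes FECa rising after 12 hours. The documents do not support that direction. Those data come from once-daily doses of 5 to 30 mg in people with working parathyroids and no second dose at 12 hours, and they show FECa below placebo up to 12 hours. A void also holds urine formed since the previous one, and the protocol does not set that interval, so a first-morning void could cover much of the same window as the pool.

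It can also be said that a 66% fall would swamp any plausible method difference. For the significance test, that is probably right. It does not protect the size of the estimate, which matters in a proof-of-principle study, and the 66% comes from six ADH1 patients with functioning parathyroid glands.

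The Table B heading refers to daily assays, but the spot row names its own two time points while neighbouring rows state Days 1-5 where that is meant. The heading does not supply the missing samples.

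**Conclusion.** The schedule and the primary endpoint do not agree. Followed as written, Section 1.3 gives no on-drug fasting spot urine for any of the up to 15 treated participants, so the endpoint in Sections 1.1, 3 and 9.4.2 cannot be computed as defined. A substitute exists but differs in kind from the baseline, and any difference between the two enters the result as apparent drug effect. Its size and direction are unknown. The rejection rates above are illustrations that rest on an assumed shift and SD, and are not estimates for this trial. If the effect is near the planning value, the test would probably still be significant, while the reported percent change could be biased. Section 9.1 offers no way out, because it conflicts with the other sections and its baseline blood is not scheduled.

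**What to change.** 1. Add to Table B, and to Table A including its existing Day 6 column, a fasting spot urine calcium and creatinine each morning on Days 2-6, before any morning dose. Collect it in the same way as the Day -1 spot and pair it with the fasting blood already drawn. Record the aliquot volume so that timed and 24-hour totals are unaffected.
2. Reconcile Section 9.1 with Sections 1.1, 3 and 9.4.2 so that one FECa definition applies.
3. Section 2.3.1 reports on the first six participants with PSH exposed to the drug, so some may lack the sample. Before analysis, pre-specify one uniform rule for them and label it a departure from the defined endpoint. One example is FECa from the Day -1 24-hour urine and the last complete on-drug 24-hour urine (Day 5, or earlier for early stoppers), each with the fasting blood at its close. This compares like with like, but the urine is mostly from fed hours, so it measures something other than the fasting spot FECa.

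The cost is a schedule amendment and a small number of routine urine assays on inpatients, with no added visit or blood draw.

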2 INTRODUCTION

2.1 Study Rationale

This study will explore the PTH-independent effects of encaleret on calcium homeostasis in patients with low or undetectable PTH levels as a result of neck surgery (post-surgical hypoparathyroidism; PSH).

Hypoparathyroidism is characterized by an inappropriately low level of PTH which results in hypocalcemia. Inadequate PTH-secretion results in lower levels of endogenous 1,25-(OH)₂ Vitamin D (decreasing calcium absorption from the gut), lower levels of calcium reabsorption in the kidney (leading to hypercalciuria), and decreased PTH-mediated bone resorption (decreasing calcium release from the bone).

Conventional therapy with oral calcium and calcitriol, often causes hypercalciuria, which is associated with long-term morbidity including nephrolithiasis, nephrocalcinosis and chronic kidney disease (Khan et al 2018, Li et al 2018). Managing patients with hypoparathyroidism is a challenging balance between increasing blood calcium while minimizing hypercalciuria (Gafni and Collins, 2019).

To avert symptoms of hypocalcemia, patients with PSH usually require a blood calcium in the normal range. This often results in hypercalciuria and renal calcification, which in some cases leads to loss of renal function, including the need for dialysis and transplantation. As such, there is a significant unmet need in treating patients with PSH.

Encaleret is a negative allosteric modulator of the calcium-sensing receptor (CaSR), also known as a calcilytic, which decreases the sensitivity of the CaSR to calcium, resulting in decreased renal calcium excretion, and in patients with intact parathyroid glands, increased PTH secretion. Pre-clinical studies have showed that calcilytics shift the IC₅₀ of the calcium-PTH curve to the right (See IB Section 4.2.3 In Vivo Studies). In cellular and animal models of both post-surgical and genetic forms of hypoparathyroidism due to CaSR gain-of-function variants, calcilytics have been shown to shift the CaSR ‘set-point’ so as to increase renal reabsorption and PTH secretion (in animals with intact parathyroid glands), resulting in increased blood calcium (Loupy et al, 2012; Dong et al, 2015; Hannan et al, 2015).

Recent and ongoing phase 2 studies of encaleret in Autosomal Dominant Hypocalcemia type 1 (ADH1) due to gain-of-function variants in the CaSR, confirm the ability of encaleret to decrease urinary calcium and raise blood calcium. However, the net effect of encaleret on urinary and blood calcium in this situation is a result of the combined effect of both renal CaSR inactivation and increased PTH signaling. Patients with ADH1 have intact and functional parathyroid glands, so there is a rapid and robust increase in PTH secretion with encaleret therapy. To understand the PTH-independent effects of encaleret on calcium homeostasis, we will study patients with PSH treated with encaleret. The results of this study may also inform the potential role of encaleret in treating patients with PSH.

While it is predicted that calcilytics will act primarily at the kidneys in PSH to increase calcium reabsorption, this study also has the potential to inform the PTH-independent effects of encaleret on other aspects of bone and mineral homeostasis, such as active vitamin D (1,25 dihydroxyvitamin D) generation from action on 1- α hydroxylase, and/or bone turnover.

There is also the theoretical possibility that encaleret may have the ability to increase PTH secretion in patients with PSH with residual but clinically insufficient parathyroid function. If this occurs, it may even be the case that encaleret treatment could restore a normal level of parathyroid function over time.

In this exploratory proof-of-principle study, patients with PSH will be treated with encaleret in order to further our understanding of the PTH-independent effects of CaSR modulation. In addition, this study may provide clinically relevant information about how encaleret could be used as either an independent or adjuvant therapy for patients with PSH.

Our primary analyses will include all participants who received at least one dose of the study drug. However, because patients with PSH have variable residual parathyroid tissue, we will also perform sub-group analyses on a “PTH-Clamp” population defined as those whose iPTH do not increase more than 10 pg/mL on encaleret and a “Aparathyroid” population defined as those whose absolute iPTH level are less than 10 pg/dl throughout the study. The biochemical response of these subpopulations may more accurately reflect the PTH-independent effects of CaSR modulation.

A small cohort of patients who developed PSH within the last year, and have not proven to have permanent PSH, will also be included in this study. These patients may have reversible parathyroid gland damage. They are included to explore whether maximal PTH stimulation by a calcilytic can transiently increase PTH secretion in healing parathyroid glands.

